## 2. SYNOPSIS

Title of Study: An Open-label Study to Assess the Safety of Repeat Administration of FX006 to Patients with Osteoarthritis of the Knee
Study Centers: Approximately 20 centers
Study Phase: 3b
Objectives: The primary objective of this study is to assess the overall safety and general tolerability of repeat administration of FX006 (two doses of 32 mg FX006) in patients with symptomatic osteoarthritis (OA) of the knee. Exploratory objectives of this study include the following: 

• examine efficacy signals for sustained pain reduction following two doses of 32 mg FX006.

• collect synovial fluid samples to enable potential future examination of synovial fluid biomarkers that may contribute to the pathogenesis of OA and/or be associated with responsiveness to FX006 treatment.

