#### **4.2.4. Adjustments for Covariates**

The exploratory continuous endpoints will include baseline score and study site as covariates. Other covariates may be explored.

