#### 4.9.1.1. Descriptive statistics, all patients

Descriptive statistics will be presented for the following groups. Each group will be displayed as a different column in the same table, in this order:

1. Patients receiving the second dose at Week 12
2. Patients receiving the second dose at Week 16
3. Patients receiving the second dose at Week 20
4. Patients receiving the second dose at Week 24
5. Patients receiving only one dose
6. All patients, first dose – all patients through patient discontinuation, study completion (through Week 12 or Week 24), or until the second dose is received (whichever happens sooner)

Descriptive statistics (number of observations, unadjusted mean, SD, median, minimum and maximum) will be presented for WOMAC A, WOMAC B, WOMAC C and WOMAC total by visit (baseline through Week 52). Change from baseline will also be presented. For the change from baseline calculation, baseline is the WOMAC result obtained on Day 1 prior to first dose.

The adjusted change from baseline will also be presented. This will be done using a longitudinal mixed effects model for repeat measures (MMRM) with fixed effects for study time point, study site and baseline score. Patient will be the random effect. The analysis will include all study visits of data. This model assumes that missing values are missing at random. This model will be run separately for each group and for WOMAC A, WOMAC B, WOMAC C and WOMAC total.

This model will be run using the SAS/STAT® PROC MIXED procedure with an unstructured correlation matrix to model the within-subject errors. If the unstructured covariance matrix does not converge when fitting the mixed model, further investigation into the most appropriate correlation matrix will be conducted. The final selection of the correlation matrix to be used in fitting the mixed model will be fully documented in the results section of the CSR.

This model will provide the baseline adjusted Least Square Means (LSM) at each visit with the corresponding standard error (SE) and associated 95% CI.

Sample SAS code that can be used to implement the mixed effects analysis is provided below:

```
proc mixed data=dsin1 method=reml;  
  by group;  
  class subjid group avisitn siteid;  
  model chg= base group avisitn siteid;  
  repeated avisitn /type=un subject=subjid;  
  lsmeans group/diff=control ('1') cl;  
run;
```

In the above code, "group" refers to the groups listed below. The model will be run for each group separately.

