A line plot presenting LSM change from baseline in WOMAC score over time will be produced. Each group will be plotted on a separate line with SE bars. Jitter will be used as needed to distinguish overlapping data.

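### The by-visit WOMAC and KOOS least-squares means in SAP 4.9.1.1 weight every site equally by default, which enlarges their standard errors; patient-based site weights would remove this at almost no cost.

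*SAP*

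**What the plan says.** SAP 4.2.4 sets the general rule: "The exploratory continuous endpoints will include baseline score and study site as covariates". Section 4.9.1.1 applies it through an MMRM with "fixed effects for study time point, study site and baseline score", and adds: "This model will be run separately for each group and for WOMAC A, WOMAC B, WOMAC C and WOMAC total". The stated output is: "This model will provide the baseline adjusted Least Square Means (LSM) at each visit", with SE and 95% CI, shown with unadjusted descriptive statistics. The results are then overlaid on one figure: "Each group will be plotted on a separate line with SE bars".

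The sample code runs BY group, lists site among the CLASS variables, and has "model chg= base group avisitn siteid" followed by "lsmeans group/diff=control ('1') cl". It uses neither the OM option (observed margins) nor AT (a chosen covariate value). The text names no site weights and no reference baseline. Section 4.9.2 analyses KOOS QOL in the same manner. The Protocol synopsis gives the number of sites: "Approximately 20 centers".

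**The concern.** With a CLASS effect for site and no OM option, LSMEANS averages the fitted site levels with weight 1/k each, where k is the number of sites contributing to that group. A site with one patient then counts as much as the largest site, and each re-dose group averages over its own set of sites.

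In a randomised comparison with no treatment-by-site term, this averaging cancels from the treatment difference. Here there is no comparator. The adjusted change at each visit is the estimate, and its SE and confidence interval carry the full cost of the weighting. The unadjusted mean in the same display is weighted by patient, so the two can differ for a reason unrelated to baseline or missing data. At stake are the precision and the reading of the main by-visit WOMAC and KOOS displays.

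**Working it through.** **Plan's own figures.** Section 4.9.1.1 states none. The only sample-size figure reproduces: 200 × 0.66 × 0.75 = 99, against a target of 100. It does not bear on this point.

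**Inputs.** From the documents: about 20 sites, about 200 enrolled, site as a fixed effect, a separate model per group. Assumed, because the documents do not give them: site sizes (gamma-distributed, CV 45%, 71% or 100%), group sizes of 30 to 190, and within-patient correlation as a random intercept (0.45) plus AR(1) (0.8).

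**One visit.** With n_j patients at site j, N in total and residual variance s²:
- patient-weighted mean: s²/N
- equal-site mean: (s²/k²) × Σ(1/n_j)

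The second is never smaller, and the two agree only when all n_j are equal. Hand example: 10 sites with 2 patients and 10 with 8 (N = 100, CV 60%). Σ(1/n_j) = 5 + 1.25 = 6.25. Variance ratio = 100 × 6.25/400 = 1.56, so the SE multiplier is 1.25.

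**Repeated visits.** The site effects are common to all visits, so only part of the excess applies:

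Var = s²/N + share × s² × [(1/k²)Σ(1/n_j) − 1/N], with share = 1/(1′R⁻¹1).

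For 13 visits the share is 0.69 (0.54 to 0.69 over the correlation structures tried). The hand example becomes 1 + 0.69 × 0.56 = 1.39, an SE multiplier of 1.18. A direct generalised least-squares calculation for the same site counts also gives 1.39.

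**Simulated site sizes** (2,000 draws per setting, median variance ratio, SE multiplier in brackets):

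| Group size | CV 45% | CV 71% | CV 100% |
|---|---|---|---|
| 190 | 1.28 (1.13) | 1.61 (1.27) | 2.04 (1.43) |
| 100 | 1.34 (1.16) | 1.52 (1.23) | 1.74 (1.32) |
| 30 | 1.21 (1.10) | 1.25 (1.12) | 1.32 (1.15) |

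At 190 this is an effective sample of 190/1.28 = 148 down to 190/2.04 = 93. The all-patients first-dose group ends by Week 24, so it has at most six post-baseline visits and a share of 0.80. Its range is then 1 + (0.80/0.69) × 0.28 = 1.32 to 1 + (0.80/0.69) × 1.04 = 2.21, or SE multipliers of 1.15 to 1.49.

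**Departure from the unadjusted mean.** In a complete-data, one-visit simulation, the patient-weighted LSM at the group's own mean baseline equalled the raw mean (largest gap 2 × 10⁻¹⁴). With complete data, site weighting is thus the only reason for the adjusted and unadjusted means to differ. For a difference between groups of 90 and 50, the empirical SD was 0.186 with equal-site weights and 0.142 with patient weights, a ratio of 1.31.

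**What the statement returns.** Under BY group each data set holds one level of group. An LSMEANS request for group returns a single mean averaged over visits, and the difference from control has nothing to compare. The by-visit means that the text promises need a request for avisitn.

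**The case against.** **Exploratory and descriptive.** Efficacy is exploratory, this section plans no between-group test, and the paired comparisons that carry p-values are unaffected. This stands and limits the consequence to precision and reading.

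**Only sample code.** The code is offered as something that may be used. But the text specifies no other weights, so software defaults would decide.

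**Equal weighting is a legitimate target.** Equal-site and patient-weighted means are different estimands. If sites were treated as a random sample, equal weighting would be more precise above an intraclass correlation of roughly 0.12 to 0.38 in the scenarios tried. The SAP treats sites as fixed and gives no reason to want an average over sites, so the loss holds under its own model.

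**A stronger reading of the label.** A reader might infer that baseline-adjusted lines on one plot have had differences in starting pain removed. They have not. With no true group difference, an assumed baseline gap of 0.4 and a slope of −0.5, the by-group LSMs still differed by −0.205, against 0.001 for one pooled model. But the SAP never claims adjustment between groups. It says that models are fitted separately, it tabulates each group's baseline, and the baseline term still does work within a group under missing at random.

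Nor does a common reference baseline follow as a requirement. The groups are formed after baseline, partly by WOMAC A itself (Protocol 7.4.3.1), so a common baseline would not make them comparable. It also costs precision. Shifting a separately fitted group by d multiplies its one-visit SE by about √[1 + N d²/((N − k) SD²)]. For N = 40 in an assumed 17 sites, d = 0.2 to 0.4 and SD = 0.7 to 0.5, that runs from √(1 + 1.74 × 0.082) = 1.07 to √(1 + 1.74 × 0.64) = 1.45. At N = 10 the multiplier is about 1.1 to 2.

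**Conclusion.** The concern holds for site weighting. As coded, the 4.9.1.1 LSMs, and KOOS with them, have an SE about 1.1 to 1.5 times that of patient-weighted LSMs for groups of 30 to 190, and they differ from the adjacent raw means partly through site weights. The size rests on assumed site imbalance and correlation. The direction needs only the fixed-site model and unequal site counts, which are near certain when about 200 patients at about 20 sites are split by re-dose week. In the one-dose group of about 10 patients (SAP section 5) the loss is small, because most sites would hold one patient.

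The documents do not support the further inference that the SAP promises between-group baseline adjustment and fails to deliver it. That point calls for a clarifying note.

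**What to change.** - **4.9.1.1 and KOOS:** replace the LSMEANS request with one for `avisitn`, using `OM=` and a data set in which every patient of the group has equal weight. Plain `OM` weights by records, so sites with better retention would count more. The MMRMs for Weeks 4, 8 and 12 in 4.9.1.2 refer back to this model and should follow it.
- **Paired models in 4.9.1.2 and 4.9.1.4:** plain `OM` suffices, because each patient contributes one record per dose. The dose differences do not change.
- **Under the adjusted-change table and plot:** state the site weights, and state that each group is evaluated at its own mean baseline and is not adjusted for baseline differences between groups.
- **Optional:** a supplementary display at a common baseline, with its loss of precision in small groups acknowledged.

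The cost is one rewritten statement, which is needed anyway to obtain means by visit, a small margins data set, one added option in the paired code, and a sentence or two of text. No new data are needed. If the sponsor prefers equal site weights, the SAP should say so and give the reason.

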#### 4.9.1.2. Change from baseline, patients receiving two doses

##### Change from Baseline to Week 12

A within patient analysis will be completed for patients who receive two doses of FX006. Change in WOMAC A, WOMAC B, WOMAC C and WOMAC total from first dose (Day 1) to Week 12 will be compared to change in WOMAC from second dose to 12 weeks after the second dose using a paired t-test.

The paired t-test will be completed by using the SAS/STAT® PROC MIXED procedure. Using the PROC MIXED procedure allows for multivariate modelling. Model covariates are study site, baseline WOMAC score, and potentially other covariates. Baseline WOMAC score for the first dose comes from the baseline visit. Baseline WOMAC score for the second dose comes from the second dose visit.

Descriptive statistics will include number of observations, unadjusted mean, standard deviation, median, minimum and maximum. Change from baseline LSM, SE and 95% CI from the mixed model will also be presented. The difference between the first dose (the control) and the second dose will be presented, and estimated via LSM from the analysis model along with 95% confidence intervals and associated 2-sided p-values. This model assumes that missing values are missing at random. Only patients that have data for both time points (i.e., change from Day 1 to Week 12 and change from the second dose to 12 weeks after the second dose) will be included in the model.

All patients who receive two doses of FX006 will be combined in the analysis and results will be displayed in the same table.

Sample SAS code that can be used to implement the analysis is provided below:

```
proc mixed data=<ADaM> method=type3;
  class subjID site arm;
  model chg = base site arm/ alpha=0.05 ddfm=kr outp=pred residual solution;
  random subjID;
  lsmeans arm / diff cl alpha=0.05;
  ods output diff=diff1 lsmeans=lsml;
run;
quit;
```

In the above code, "arm" refers to the first or second dose administered (coded as a 1 or 2).

The analysis above will also be performed to compare the changes in WOMAC A, WOMAC B, WOMAC C and WOMAC total from first dose (Day 1) to Week 12 to the changes from first dose (Day 1) to 12 weeks after the second dose.

#### Change from Baseline to Week 4, 8 and 12

A second analysis will be completed for patients who receive two doses of FX006. Change in WOMAC A, WOMAC B, WOMAC C and WOMAC total from first dose (Day 1) to Week 4, Week 8 and Week 12 will be presented alongside change in WOMAC from second dose to 4, 8 and 12 weeks after the second dose.

This will be done using a longitudinal MMRM as described in section 4.9.1.1 with fixed effects for study time point (Week 4, Week 8 and Week 12), study site and baseline score. Patient will be the random effect. The analysis will include all study visits of data (Week 4, 8 and 12) through Week 12. This model assumes that missing values are missing at random. Separate models will be run for the first and second doses.

This model will be run using the SAS/STAT® PROC MIXED procedure with an unstructured correlation matrix to model the within-subject errors. If the unstructured covariance matrix does not converge when fitting the mixed model, further investigation into the most appropriate

correlation matrix will be conducted. The final selection of the correlation matrix to be used in fitting the mixed model will be fully documented in the results section of the clinical study report.

This model will provide the adjusted LSM estimates at each visit with the corresponding standard error and associated 95% confidence interval.

In addition to change from baseline, descriptive statistics for the unadjusted observed WOMAC values will also be tabulated.

The same analysis that is described above for change from baseline will also be performed for percent change from baseline. Percent change from baseline will be calculated as follows:

$$\text{Percent change from BL} = (\text{Value} - \text{BL value})/\text{BL value} * 100$$

Line plots presenting observed, LSM change and LSM percent change from baseline in WOMAC A, WOMAC B, WOMAC C and WOMAC total score over time will be produced. In these plots, Week 4, Week 8 and Week 12 as well as 4, 8 and 12 weeks after the second dose, will be presented. There will be a separate line for the first and second dose along with standard deviation bars for observed values and standard error bars for adjusted values. LSM change from baseline and percent change from baseline will come from separate mixed models as described above.

The analysis above will also be done where change in WOMAC A, WOMAC B, WOMAC C and WOMAC total from first dose (Day 1) to Week 4, Week 8 and Week 12 will be presented alongside change in WOMAC from first dose (Day 1) to dose to 4, 8 and 12 weeks after the second dose.

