**4.2.10.      Baseline Definitions**

Baseline for the first dose is the baseline/Day 1 assessment prior to administration of the first dose of study treatment. If the baseline result is missing, the last non-missing result prior to administration of study treatment may be used from the Screening period.

Baseline for the second dose of study treatment is defined as the last data collected prior to the second dose of study treatment administration. This is the same study visit, as long as the data are collected prior to the second dose.

Where noted in this SAP, change from baseline for efficacy analyses are also performed where baseline for the second dose is defined as the baseline/Day 1 assessment prior to administration of the first dose of study treatment.

Additional baselines may be defined to explore efficacy endpoints comparing the first dose and the second dose of study treatment administration. All new baseline definitions will be fully specified and documented in an interim SAP (iSAP) and in the final CSR.

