#### 4.9.1.4. Area Under the Effect Curve (AUE) for Change from Baseline in WOMAC over Time

The Area Under the Effect curve (AUE) for change from baseline in WOMAC A, B, C and total score over various time intervals will be examined.

AUE will be calculated from a linear trapezoidal rule using the following formula for change from baseline in WOMAC A, WOMAC B, WOMAC C and WOMAC total:

$$AUE_{t_i-t_{i+n}} = \sum_{t_i}^{t_{i+n}} ((WD_i + WD_{i+1})/2) * (t_{i+1} - t_i)$$

Where  $WD_i$  = WOMAC difference (change) from baseline in WOMAC score for time  $t_i$ , and  $WD_{i+1}$  = WOMAC difference (change) from baseline in WOMAC score for time  $t_{i+1}$ , over the time interval  $t_i$  to  $t_{i+1}$ . (Note that the difference for  $t_{i+1} - t_i$  will be 4 week intervals). Only non-missing time intervals will be part of the sum for each AUE calculation (Farrar et al. 2000). Baseline for the first dose will be used for all WOMAC difference from baseline calculations.

Two within patient analyses will be completed for patients who receive two doses of FX006. In the first analysis, the AUE for the change from baseline for the first dose from Week 4 to Week 12 will be compared to the AUE for the change from baseline for the second dose from 4 to 12 weeks after the second dose for all patients. In the second analysis, the AUE for the change from baseline for the first dose from Week 4 to the second dose will be compared to the AUE for the change from baseline for the second dose from 4 weeks after the second dose to the comparable period after the second dose.

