##### Comparison of change from baseline to Week 12 for the first and second doses

AUE for WOMAC A, WOMAC B, WOMAC C and WOMAC total change from baseline for the first dose from Week 4 Week 12 will be compared to AUE for WOMAC A, WOMAC B, WOMAC C and WOMAC total for the change from baseline for the second dose from 4 to 12 weeks after the second dose using a paired t-test. The examination of WOMAC A (Pain) will be an indication of the durability of the pain relief response, where WOMAC B (Stiffness) and WOMAC C (Function) will provide an indication of the durability of the responses for these two sub-scales over the course of two doses.

The paired t-test will be completed by using the SAS/STAT® PROC MIXED procedure. Model covariates are study site, baseline WOMAC score, and potentially other covariates. Baseline WOMAC score for the first dose comes from the first dose visit. Baseline WOMAC score for the second dose comes from the second dose visit. Sample SAS code provided in section 4.9.1.2 will be used.

Descriptive statistics will include the LSM and standard error, 95% confidence interval, LSM difference from control (first dose Week 4 to Week 12), and 2-sided p-value. This model assumes missing at random and only includes observed data; missing data are not imputed in

this model. Only patients that have data for both time points (i.e., first dose Week 4 to Week 12 and second dose Week 4 to Week 12) will be included in the model.

All patients who receive two doses of FX006 will be combined in the analysis and results will be displayed in the same column.

The analysis above will also be performed where baseline for the second dose is defined as the baseline/Day 1 assessment prior to administration of the first dose of study treatment.

Comparison of change from baseline to second dose and change from second dose to comparable period after second dose

AUE for WOMAC A, WOMAC B, WOMAC C and WOMAC total change from baseline for the first dose from Week 4 to the second dose will be compared to the AUE for WOMAC A, WOMAC B, WOMAC C and WOMAC total change from baseline for the second dose from 4 weeks after the second dose to the comparable period after the second dose using a paired t-test.

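### In the comparisons where both doses are measured from Day 1, the covariate for dose 2 is (AUE) or may be (12-week change) the second-dose-visit score, which can shift the dose contrast.

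*SAP*

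**What the plan says.** SAP 4.9.1.2 compares, within patients who had two doses, the 12-week change after dose 1 with the 12-week change after dose 2. The sample code is "model chg = base site arm/ alpha=0.05 ddfm=kr outp=pred residual solution" with a random patient effect, so there is one slope for `base` across both doses. For dose 1, `base` is the score at the baseline visit. For dose 2: "Baseline WOMAC score for the second dose comes from the second dose visit". A rerun follows: "The analysis above will also be performed to compare the changes in WOMAC A" and the other WOMAC scores "from first dose (Day 1) to Week 12 to the changes from first dose (Day 1) to 12 weeks after the second dose". That restates the outcome but not the covariate.

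SAP 4.9.1.4 (AUE) says: "Baseline for the first dose will be used for all WOMAC difference from baseline calculations". Both AUE comparisons then repeat the covariate sentence that points to the second-dose visit and borrow the code of 4.9.1.2. Each also ends with a rerun: "The analysis above will also be performed where baseline for the second dose is defined as the baseline/Day 1 assessment".

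SAP 4.2.10 adds a general rule. Where the SAP notes it, change from baseline is also analysed "where baseline for the second dose is defined as the baseline/Day 1 assessment prior to administration of the first dose of study treatment".

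For the Week 4, 8 and 12 repeated-measures analysis: "Separate models will be run for the first and second doses".

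**The concern.** A Day 1-based comparison asks whether dose 2 brings the patient to the same level as dose 1 did. If `base` is the Day 1 score in one record and the second-dose-visit score in the other, the least-squares means compare the doses at equal `base`, although the two records carry scores from different times. For a patient re-dosed at Week 12, the dose 2 covariate is the score that determines the dose 1 outcome, and it is also the last point of the dose 1 AUE. The adjustment then removes part of a treatment effect from one side only.

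The SAP reports the adjusted difference with a p-value and calls p ≤ 0.05 statistically significant and potentially informative (4.2.1). It makes no multiplicity adjustment (4.2.5), allows interim results for publication and regulatory updates (4.3), and takes the AUE result as an indication of durability over two doses (4.9.1.4). An artefact here could therefore be reported as a finding.

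The main run of 4.9.1.2, where outcome and covariate both start at the second-dose visit, is not part of this point.

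**Working it through.** **Planning figure.** 200 × 0.66 × 0.75 = 99, against at least 100 (SAP 4.1). It reproduces within rounding. The documents give no power calculation and no figure for this contrast.

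**Algebra.** Each patient has two records, and site is the same in both. The fitted dose contrast is therefore

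contrast = mean paired difference in outcome − slope × (mean `base` for dose 2 − mean `base` for dose 1).

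- Day 1 score in both records: the bracket is 0 and the contrast equals the mean paired difference.
- Second-dose-visit score for dose 2: the bracket is the gap, so the shift is −slope × gap.

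**Sign of the gap.** Re-dosing requires benefit from dose 1 (protocol 7.4.3.1), which makes a negative gap plausible. But entry and re-dosing use the same WOMAC A threshold of 6, and re-dosing also accepts a clinical rationale. The documents therefore fix neither the size nor the sign of the gap.

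**Simulation.**
- From the SAP: the 4.9.1.2 model, the 0-4 scale and two-sided 0.05.
- From the protocol synopsis: 20 sites.
- n = 100 (the plan) and n = 135 = 200 × 0.90 × 0.75, using the re-dosing share of more than 90% in SAP section 5.
- Assumed: SD 0.7; 12-week correlation 0.4 to 0.6, either constant or decaying with time; dosing all at Week 12, mixed 40/30/20/10% over Weeks 12/16/20/24, or all after Week 12; gap 0 to -1.0.
- The same mean level is reached at matching times after each dose, so the true difference is 0.
- REML replaced the type 3 method, with 300 to 400 simulated trials per setting.

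12-week change, second-dose-visit covariate. The last column is the share of trials in which dose 2 is falsely significantly better (nominal 2.5%).

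| n | Dosing | Gap | False difference | Share |
|---|---|---|---|---|
| 100 | all Week 12 | -0.4 | -0.10 to -0.17 | 27-61% |
| 100 | all Week 12 | -0.7 | -0.15 to -0.29 | 47-96% |
| 100 | mixed | -0.4 | -0.04 to -0.10 | 8-21% |
| 100 | mixed | -0.7 | -0.08 to -0.18 | 13-47% |
| 100 | all after Week 12 | -0.7 | -0.04 to -0.13 | 5-25% |
| 100 | any | 0 | none | 1-5% |
| 135 (correlation 0.5) | mixed | -0.4 | -0.07 to -0.09 | 16-27% |
| 135 (correlation 0.5) | mixed | -0.7 | -0.13 to -0.15 | 39-57% |

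Check against the formula (n = 135, all at Week 12, constant correlation, gap -0.7, fitted slope -0.370): −(−0.370)(−0.7) = −0.259. The simulation gave −0.258.

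AUE, Weeks 4 to 12, n = 100, correlation 0.5, gap -0.7, in score-weeks:

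| Dosing | Constant correlation | Decaying correlation |
|---|---|---|
| all Week 12 | -0.97 (60%) | -0.20 (5%) |
| mixed | -0.71 (32%) | +0.25 (1%) |
| all after Week 12 | -0.56 (23%) | +0.59 (0%) |

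Percentages again count only dose 2 falsely better. Under decaying correlation the second-dose-visit score tracks the scores that follow it more closely than it tracks Day 1, so the slope can turn positive. For mixed dosing: −(0.366)(−0.7) = +0.256, against +0.249 simulated.

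**Day 1 covariate for both doses.** The 12-week difference is within 0.01 of 0, with dose 2 falsely better in about 0.5% to 5% of trials. The AUE difference is within 0.04 score-weeks of 0, with 1.5% to 3.3%.

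**Selection on the score.** The tables do not model it. A further simulation did, re-dosing at a score of 6 or more out of 20, or by rationale at an assumed 25% chance. Its mean gap was -0.62 to -0.72 and its false 12-week difference -0.04 to -0.19; with the Day 1 covariate it was 0.00.

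**The case against.** The strongest reply is that the SAP already provides for this. In 4.2.10 the baseline for dose 2 becomes Day 1 wherever the SAP notes it, and the covariate in 4.9.1.2 is named with the same term. The rerun could count as such a note. This stands as a possible reading, so a reader should not infer that the 12-week rerun certainly keeps the second-dose-visit covariate. But the 4.2.10 sentence is about change from baseline, and 4.9.1.2 never says that the covariate moves. Two programmers could produce different p-values from this text.

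For AUE, the reply is that the reruns are the matched analysis. If every difference already starts at Day 1, only the covariate is left for the rerun to change. That is a fair inference, so it would be wrong to say that no matched AUE analysis is planned. It also confirms that the main AUE run is mismatched. To avoid that, one would have to read the main dose 2 outcome as starting at the second-dose visit, against the statement that the first-dose baseline serves for all differences. The SAP does not say whether the reruns change outcome, covariate or both.

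It is also fair that efficacy is exploratory, that 4.9.1.2 reports unadjusted means alongside, and that the size of the shift rests on assumed inputs. Nor is equal `base` impossible for an individual: a patient whose pain has returned to the Day 1 score has it.

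**Conclusion.** The point holds in a conditional form. The mismatch is explicit in the main AUE models. In the Day 1 rerun of 4.9.1.2 it is the literal reading, but not the only one. Where it applies, the contrast is shifted by −slope × gap. If the second-dose-visit score is on average below Day 1, the 12-week contrast tends to favour dose 2 even when both doses reach the same level.

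Two stronger conclusions are tempting and not supported:

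- That an identical second dose will look significantly better. The rate runs from nominal to nearly certain, depending on gap, dosing weeks, correlation and the number of pairs analysed. Apart from the planned number of patients, the documents give none of these.
- That AUE is always biased towards dose 2. The shift can be nearly absent or reversed.

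Identical here means the same level reached. If it meant the same fall from the pre-dose score, a Day 1-based contrast would favour dose 2 whenever the gap is negative, whatever the covariate.

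The Week 4, 8 and 12 analysis fits separate models per dose without a test between them and is not affected. Nor is the primary safety objective.

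**What to change.** - In SAP 4.9.1.2 and 4.9.1.4, state that whenever the outcome is change from Day 1 for both doses, `base` is the Day 1 score for both doses, so that the contrast equals the paired difference. Remove the second-dose-visit covariate from those models.
- In 4.9.1.4, state for each rerun whether outcome, covariate or both change. Once the main AUE model uses Day 1 throughout, a rerun that changes only the covariate duplicates it and can go. If the main run was meant to start dose 2 at the second-dose visit, the sentence on the first-dose baseline needs amending instead.
- KOOS QOL is analysed like WOMAC under 4.9.1.2 (SAP 4.9.2), so the clarification should cover it too.

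The cost is a few sentences and one variable in the analysis data set, with no new data. It should be settled before database lock.
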